This study is designed to assess the safety and immunogenicity of one or two doses of the Sing2016 M2SR H3N2 influenza vaccine delivered intranasally. Eligible participants will be enrolled and randomly assigned to receive the Sing2016 M2SR H3N2 vaccine (one or two doses) or placebo. An overview of the planned cohorts is presented in [Table 2](#). All participants will be administered the IIV4 seasonal influenza vaccine a minimum of 28 days after last IP dose or later once it is available (anticipated September – November). IIV4 may be administered outside of the study window described in the protocol, in case of public health emergency or as determined necessary by institutional policy, regulatory authorities, sponsor or principal investigator. Management of participants who meet this criterion will be as determined suitable by site-specific procedures. COVID-19 vaccines which are fully approved or approved under EUA may be received during study participation. COVID-19 vaccines may not be received within the 10 days before receipt of the study product nor planned to be received during a reactogenicity period (the day of and 7 days following each intranasal vaccination) of the study product. Participants who experience a COVID-19 exposure during study participation will be managed as per institutional protocol.

Due to the limited availability of product, and funding to support additional years of enrollment into Cohorts 5, 6, and 7, the decision was made to stop enrollment after the final participant was enrolled into Cohort 4.

Table 2. Cohorts

Cohort	Age	Experience	Vaccine	Dose	Doses	Participants
1	9-17 yrs.	Non-naive	Sing2016 M2SR H3N2	10^9 TCID ₅₀	1	30
			Placebo	-	1	15

2	2-8 yrs.	Non-naïve	Sing2016 M2SR H3N2	10^8 TCID ₅₀	1	30
			Placebo	-	1	15
3	2-8 yrs.	Non-naïve	Sing2016 M2SR H3N2	10^9 TCID ₅₀	1	15
			Placebo	-	1	10
4	2-8 yrs.	Non-naïve	Sing2016 M2SR H3N2	10^9 TCID ₅₀	2	15
			Placebo	-	2	10
5	6-23 mo.	Naïve	Sing2016 M2SR H3N2	10^7 TCID ₅₀	2	6
			Placebo		2	2
6	6-23 mo.	Naïve	Sing2016 M2SR H3N2	10^8 TCID ₅₀	2	18
			Placebo	-	2	8
7	6-23 mo.	Naïve	Sing2016 M2SR H3N2	10^9 TCID ₅₀	2	18
			Placebo	-	2	8
Total Sample size					200	

Schedule of assessments can be found in [Section 1.2, Schedule of Activities](#).

Protocol Schema can be found in [Section 1.3, Protocol Schema](#).

Dose escalation or dose-ranging details are found in [Section 6.1.2, Dosing and Administration](#)

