5. GENERAL STATISTICAL CONSIDERATIONS

5.1. General Principles

For screening and baseline visits, the last assessment value obtained prior to the first vaccination/dose of study product will be used. If participants completed assessments at both scheduled and supplementary visits, the assessments from the scheduled visit will be considered in the statistical analyses, tabular summaries, and figures. However, if an assessment is completed only at supplementary visits, then the assessment from the earliest supplementary visit occurring after the scheduled visit will be included in the statistical analyses, tabular summaries, and figures. Results of all assessments, including those performed during supplementary visits, will be included in the listings.

Generally, summaries will be presented by cohort and vaccination group (i.e., 9-17 yrs, 10^9 TCID₅₀ Sing2016 M2SR, 1 Dose; 9-17 yrs, Placebo, 1 Dose; 2-8 yrs, 10^8 TCID₅₀ Sing2016 M2SR, 1 Dose; etc., called “analysis group” throughout the SAP). Post-first dose safety results for participants in Cohorts 3 and 4 receiving active vaccine may be combined as both cohorts receive the same dose and belong to the same age group.

For descriptive analyses, continuous variables will be summarized by the non-missing sample size, mean, standard deviation (SD), and the minimum, median, and maximum. Categorical variables will be summarized by frequencies and percentages of observed levels, based on the non-missing sample size. When calculating incidence, or any sub-classification thereof (e.g., by study vaccination, time period, severity, relatedness, etc.) each participant will only be counted once at the maximum value of the respective variable (e.g., maximum severity, maximum relatedness, etc.), and any repetitions will be ignored. All tables will be annotated with the analysis population and the total population size relevant to that table, including any missing observations. Data listings will typically be sorted by cohort (even if not presented), vaccination group, site, participant, and visit number within participant, where appropriate.

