5.3.4. Modified Intent to Treat (mITT) Population

The Modified Intent-to-Treat (mITT) population will consist of all participants who received study influenza vaccination and have a baseline and at least one post-baseline sample available. Immunogenicity analyses will be performed utilizing the mITT population.

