5.3.5. Per-Protocol (PP) Population

The Per-Protocol (PP) population will include participants in the mITT population with the following exclusions of data:

- Data from participants determined to be ineligible at baseline (determined thereafter)
- Data from participants in Cohorts 4, 5, 6, and 7 subsequent to missed second study vaccinations
- Data from Visit 4 for Cohorts 1-3, from Visit 4C for remaining cohorts, and from Visit 6 for all cohorts if the corresponding visit occurred substantially out of window
- Data from all visits subsequent to major protocol deviations that could impact the validity of later data, such as:
 - Receipt of immunosuppression or any medications that may be associated with impaired responsiveness
 - Receipt of any non-study investigational drug/investigational vaccine/licensed vaccine outside of what is allowable per-protocol
 - Receipt of incorrect study influenza vaccination, including incorrect dosage

Visit 4, 4C, and 6 will be considered substantially out of window if they occur more than ± 15 days from the target day (i.e., more than 500% of the half width of the visit window days from the target day).

If sufficient data (>10% of secondary analysis timepoints) would be excluded by the PP exclusions, sensitivity analyses will be performed utilizing the PP population for secondary immunogenicity analyses.

Sensitivity analyses will be performed according to the study influenza vaccination received if a sufficient number of participants receive the study influenza vaccination discrepant (e.g., the wrong vaccine or the wrong dose) from what was indicated per randomization.

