7.1. Secondary Immunogenicity Analyses

Hemagglutination inhibition (HAI) and microneutralization (MN) antibody titers are measured in serum against A/Singapore/INFIMH-16-0019/2016. These antibody titers will be summarized by geometric mean titers (GMTs) and the percentage of participants reporting titers $\geq 1:40$ (defined as seroprotection for HAI) and associated 95% CIs, presented by analysis group at baseline and 28 days post last vaccination (Day 29 for Cohorts 1-3, Day 57 for Cohort 4). Geometric mean fold-rise (GMFR) and the percentage of participants reporting a fold-rise ≥ 2 and ≥ 4 from baseline and associated 95% CIs will also be presented for visits post baseline ([Table 13](#) and [Table 14](#) for HAI and MN, respectively). Titers will be presented graphically over time via line graphs displaying the GMT and associated 95% CIs for each analysis group with individual trajectories presented at a decreased transparency ([Figure 3](#) and [Figure 4](#) for HAI and MN in serum, respectively).

ECL signal, total sIgA concentration, and specific activity (as defined in [Section 3.3](#)) are measured in NLF supernatant by BAMA will be summarized at baseline, 28 days post last study vaccination, and 28 days post IIV4 administration, separately for each antigen. Arithmetic means and associated 95% CIs will be presented for ECL signal, total sIgA concentration, and specific activity by analysis group at baseline and 28 days post last vaccination (Day 29 for Cohorts 1-3, Day 57 for Cohort 4). Arithmetic mean difference from baseline and associated 95% CIs for ECL signal, total sIgA concentration, and specific activity will also be presented for visits post baseline ([Table 15](#) through [Table 18](#)). ECL signal, total sIgA concentration, and specific activity as measured by BAMA will be presented graphically over time, separately by antigen, via line graphs displaying the arithmetic mean and associated 95% CIs for each analysis group with individual trajectories presented at a decreased transparency ([Figure 5](#) through [Figure 7](#)).

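### No SAP rule keeps a sample drawn after IIV4 out of the Day 29/57 mITT summaries; the protocol's order of procedures protects only draws made as scheduled.

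*SAP*

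**What the plan says.** **Sample selection.** SAP 5.1 prefers the scheduled visit. If the assessment was done only at supplementary visits, "then the assessment from the earliest supplementary visit occurring after the scheduled visit will be included in the statistical analyses".

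**Main analysis set.** SAP 5.3.4 states: "Immunogenicity analyses will be performed utilizing the mITT population". Membership covers "all participants who received study influenza vaccination and have a baseline and at least one post-baseline sample available". Visit windows and IIV4 play no part.

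**Per-protocol set.** SAP 5.3.5 removes Visit 4, 4C or 6 data when the visit is "more than 500% of the half width of the visit window days from the target day", given there as 15 days. Its vaccine item is "Receipt of any non-study investigational drug/investigational vaccine/licensed vaccine outside of what is allowable per-protocol". The set is used for sensitivity analysis only, and only if more than 10% of secondary timepoints would be excluded.

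**IIV4 timing.** Footnote 11 of the Schedule of Activities (Protocol 1.2, repeated in SAP Table 1) allows IIV4 from 28 days after the last intranasal dose. That includes Visit 4 for Cohorts 1-3 and Visit 4C for Cohort 4, and dates before September 1. The same footnote requires the other study procedures to be finished first. Protocol 4.1 adds that "IIV4 may be administered outside of the study window described in the protocol" in a public health emergency, or where an institution, regulator, the sponsor or the investigator finds it necessary.

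**Timepoints.** For serum HAI and neutralization, SAP 7.1 makes Day 29 (Cohorts 1-3) and Day 57 (Cohort 4) the secondary timepoints. SAP 7.2 treats 28 days after IIV4 as a separate, exploratory one.

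**The concern.** The Day 29/57 summaries are meant to describe the response to the study vaccine or placebo. IIV4 contains influenza antigen and gets its own timepoint because it may change the same titres. A sample drawn after IIV4 but counted as Day 29 or Day 57 measures IIV4, or both vaccines together. It could raise the GMT, the GMFR and the responder percentages of the group it falls in.

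The inclusion rule in SAP 5.1 is mandatory, so the statistician has no stated ground for leaving such a value out of the main analysis. Groups of 10 to 30 children give a single value visible weight.

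**Working it through.** **1. The plan's own limit.** The Visit 4 window is Day 26 to 32, so the half-width is (32 - 26)/2 = 3 days. Visits 4C and 6 run from +25 to +31 days, so (31 - 25)/2 = 3 days. Then 500% × 3 = 15 days, as SAP 5.3.5 states.

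**2. What that limit lets through.** The latest sample kept in the per-protocol set is Day 29 + 15 = Day 44 (Cohorts 1-3), or V4 + 28 + 15 = V4+43 (Cohort 4). The earliest ordinary IIV4 is Day 1 + 28 = Day 29, or V4+28. A sample up to 44 - 29 = 15 days after IIV4 therefore passes. In the mITT set there is no cut-off.

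**3. The three situations.**

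| Situation | mITT | Per-protocol set |
|---|---|---|
| Draw made as scheduled at Visit 4/4C, IIV4 afterwards | Sample precedes IIV4; no problem | Same |
| Draw missed or failed, IIV4 given, supplementary draw later | Included, whatever the delay | Dropped only if more than 15 days from target |
| IIV4 given outside its window before the Day 29/57 draw | Included | 15-day limit does not help if the draw itself is on time |

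The listed per-protocol vaccine item does not reach the last two rows. It concerns non-study products beyond what the protocol allows, while IIV4 is study Product 4 and its use is allowed.

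**4. When the per-protocol analysis is run.** Planned enrolment in Cohorts 1-4 is 45 + 45 + 25 + 25 = 140. With one secondary post-baseline timepoint per child, more than 14 of 140 must be excluded. If baseline is counted too, it is more than 28 of 280. A handful of post-IIV4 samples would not trigger it.

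**5. Effect of one child.** Suppose IIV4 multiplies one child's titre by f and nothing else changes. The group GMT and GMFR are then multiplied by f^(1/n), and at most one responder is added, which is 100/n percentage points. The documents give no value for f, so 4 to 16 is an assumption.

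| n | Groups (planned size) | f = 4 | f = 8 | f = 16 | Added to 4-fold responder rate |
|---|---|---|---|---|---|
| 30 | Vaccine, Cohorts 1 and 2 | 1.05 | 1.07 | 1.10 | at most 3.3 points |
| 15 | Vaccine, Cohorts 3 and 4; placebo, Cohorts 1 and 2 | 1.10 | 1.15 | 1.20 | at most 6.7 points |
| 10 | Placebo, Cohorts 3 and 4 | 1.15 | 1.23 | 1.32 | at most 10 points |

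**6. Against sampling error.** If nobody truly responds, the exact 95% upper limits are 11.6% (0/30), 21.8% (0/15) and 30.8% (0/10), matching SAP Table 4. One false responder gives 3.3% (0.1 to 17.2), 6.7% (0.2 to 31.9) and 10.0% (0.3 to 44.5). The shift is real but lies well inside the uncertainty already present.

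**The case against.** **The order rule.** The strongest reply is footnote 11: IIV4 waits until the other procedures are complete. A reader might infer that nothing at all separates IIV4 from the endpoint sample. The documents do not support that, because a scheduled draw at Visit 4/4C comes first. This part of the reply stands. But the footnote instructs sites and does not select data. It does not say whether IIV4 is withheld after a failed draw. Only the pre-vaccination blood is a condition of taking part, and SAP Table 5 lists uncollected blood, uncollected nasal specimens and missed visits as deviation types. Protocol 4.1 neither repeats nor waives the order.

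**The per-protocol set.** A reader might also infer that a post-IIV4 sample always survives in both sets. It does not. Dosing may begin on March 1 and IIV4 usually comes in September to November. For a child dosed in spring, a post-IIV4 sample would typically be months late and beyond the 15-day limit. The exposed children are those whose Visit 4/4C falls close to their IIV4. The list of major deviations is also open-ended, so IIV4 before the draw could be classed as one. That would be a judgement made later, in an analysis that may not be run.

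**Visit 6.** It is a scheduled visit with its own timepoint, so SAP 5.1 does not move its values to Day 29/57.

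**Masking.** A reader might infer that contamination would hide a vaccine-placebo difference. This is not shown. Both arms receive IIV4, allocation is randomised and blinded, and nothing suggests that affected samples would gather in placebo. The titres are against A/Singapore/INFIMH-16-0019/2016, and the documents do not name the H3N2 strain in the IIV4 used, so even the rise is assumed.

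**Other safeguards.** Supplementary results are listed, deviations are tabulated and implausible values are investigated. These make a problem visible but do not change which value enters the main table.

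**Conclusion.** The gap is real but narrow. SAP 5.1 and the mITT definition together require a post-IIV4 supplementary sample to be counted as Day 29 or Day 57, and they also admit an on-time sample from a child given IIV4 early under Protocol 4.1. The per-protocol analysis is only a partial and conditional backstop.

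The number of affected children cannot be derived from the documents and is probably very small; it may be zero. Under the assumed 4- to 16-fold rise, one child moves a group GMFR by between 5% (n=30, 4-fold) and 32% (n=10, 16-fold), and a 4-fold responder rate by at most 3.3 to 10 points, in whichever arm the child belongs to. The gap also covers the nasal sIgA endpoints, but the documents give no basis for a size there. This is a minor clarification worth making, not a threat to the trial's conclusions, which are descriptive.

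**What to change.** 1. Add to SAP 5.1: *A sample contributes to the Day 29 (Cohorts 1-3) or Day 57 (Cohort 4) summaries only if it was drawn before IIV4. Otherwise that timepoint is missing, the value appears only in Listing 10 with a flag, and the number of values dropped is reported by analysis group.* Same-day samples at Visit 4/4C can be taken as preceding IIV4 under the order rule unless a deviation is recorded.
2. Add to the per-protocol exclusions in SAP 5.3.5: *IIV4 received before the Day 29/57 sample.*
3. State in SAP 5.3.5 that the existing 15-day limit applies to supplementary samples standing in for Visit 4, 4C or 6.

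The cost is a few sentences and a flag in the Listing 10 shell, which has no place for such a value now. The rule uses only IIV4 and sampling dates, which the 28-days-post-IIV4 timepoint already requires. It does not depend on titres or arm, so it cannot be tuned to results. At most a few values become missing, and SAP 5.5 already plans no imputation. No change to IIV4 timing or to any clinical procedure is proposed.

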5.2. Timing of Analyses

The interim analysis was performed after all participants completed through 28 days post-first vaccination.

After clinical database lock and receipt of secondary immunogenicity data, a set of topline tables will be generated by the Statistical and Data Management Coordinating Center (SDMCC), including summaries of clinical safety and secondary immunogenicity data. These analyses will be considered final and will be included in the Clinical Study Report (CSR) as well. The CSR, comprised of the final analyses of safety and available immunological data, will be subsequently completed. Any available data from the exploratory endpoints may also be included. Additional exploratory endpoint data not available at the time of CSR

preparation may be included in one or more addenda to the CSR, manuscript(s), or other report. Plans for remaining analyses will be included in an addendum to the SAP with results presented in an addendum to the CSR after those data are available.

5.3. Analysis Populations

Analyses will be conducted within one of the following populations.

5.3.1. Screened Populations

The Screened population will include all participants screened. This population will be used for summaries relating to screen failures.

5.3.2. Enrolled Population

The Enrolled population will include all participants enrolled and randomized. This population will be used for summaries of participant disposition as well as participant demographics and baseline characteristics.

5.3.3. Safety Population

The Safety population will include all participants who receive at least one study influenza vaccination. This population will be used for analyses of adverse events and reactogenicity.

5.3.4. Modified Intent to Treat (mITT) Population

The Modified Intent-to-Treat (mITT) population will consist of all participants who received study influenza vaccination and have a baseline and at least one post-baseline sample available. Immunogenicity analyses will be performed utilizing the mITT population.

5.3.5. Per-Protocol (PP) Population

The Per-Protocol (PP) population will include participants in the mITT population with the following exclusions of data:

- Data from participants determined to be ineligible at baseline (determined thereafter)
- Data from participants in Cohorts 4, 5, 6, and 7 subsequent to missed second study vaccinations
- Data from Visit 4 for Cohorts 1-3, from Visit 4C for remaining cohorts, and from Visit 6 for all cohorts if the corresponding visit occurred substantially out of window
- Data from all visits subsequent to major protocol deviations that could impact the validity of later data, such as:
 - Receipt of immunosuppression or any medications that may be associated with impaired responsiveness
 - Receipt of any non-study investigational drug/investigational vaccine/licensed vaccine outside of what is allowable per-protocol
 - Receipt of incorrect study influenza vaccination, including incorrect dosage

Visit 4, 4C, and 6 will be considered substantially out of window if they occur more than ± 15 days from the target day (i.e., more than 500% of the half width of the visit window days from the target day).

If sufficient data (>10% of secondary analysis timepoints) would be excluded by the PP exclusions, sensitivity analyses will be performed utilizing the PP population for secondary immunogenicity analyses.

Sensitivity analyses will be performed according to the study influenza vaccination received if a sufficient number of participants receive the study influenza vaccination discrepant (e.g., the wrong vaccine or the wrong dose) from what was indicated per randomization.

5.4. Subgroups, Interactions and Covariates

The protocol does not define and is not powered for any formal subgroup analyses. Conditional post-hoc exploratory analyses will be performed for subgroups as outlined in [Section 7.2](#).

5.5. Missing Data and Outliers

No imputation is planned for missing data.

Any data point that appears to be erroneous or inexplicable based on the observed data distribution and the statistical team's understanding of the analysis variables will be investigated as a possible outlier. If data points are identified as outliers, sensitivity analyses may be performed to examine the impact of including or excluding the outliers. Any substantive differences in these analyses will be reported.

5.6. Interim Analyses and Data Monitoring

5.6.1. Interim Analyses

An interim analysis focused primarily on immunogenicity was conducted while the study was ongoing. These analyses, including primary, secondary, and exploratory endpoints, were made available to the pharmaceutical partner for planning for future studies, with no public dissemination of results, and were not used to make any decisions concerning the conduct of this trial. Immunogenicity specimens (serum, plasma, nasal washes) collected through the Day 29 visit (Visit 4) for Cohorts 1 to 3 and through Day 57 visit (Visit 4C) for others were presented in aggregate by cohort and vaccine/placebo where data were available. Participant-level immunogenicity data were not presented to maintain the blind. Interim safety analyses through the Day 29 visit (Visit 4) for Cohorts 1 to 3 and through Day 57 visit (Visit 4C) for others were presented aggregated by cohort, to avoid the possibility of unblinding due to rare adverse events occurring only in active vaccine or placebo groups.

5.6.2. Data Monitoring Committee

Two safety committees were convened for this study: the Safety Review Committee (SRC) and the Safety Monitoring Committee (SMC).

The SRC reviewed blinded safety data to allow for progression through the cohorts as described in the protocol (Section 4.1). The SMC reviewed safety data if criteria for progression to enrollment of a subsequent cohort was not met, a halting rule (as outlined in the protocol, Section 1.1) occurred, or as regularly scheduled per the separate SMC charter.

SMC reviews were blinded to study assignment, with unblinded study assignments available upon SMC request. As an outcome of each SMC review, the SMC made a recommendation to continue, modify, or terminate the study.

Interim safety reviews included a summary of halting rules, demographic information, participant disposition, AEs, SAEs, AESIs, NOCMCs, and protocol deviations as per the mock TLF shells provided in a separate document.

